6.1 DETERMINATION OF SAMPLE SIZE

[figure not shown]
Assuming a) the expected proportion of patients who will be event free during 96 weeks is 45%; b) the type one error rate is 5% and the half-width of 95% CI for the proportion is 4%; c) the probability that half-width of 95% CI is at most 4% is 80%, then the required sample size will be $n=600$.

It should be noted that the estimation of the proportion of patients who will be protocol-defined event free (45%) is based on the pooled data from Studies WA21092 and WA21093 (OPERA I and OPERA II, respectively) from all patients who had a baseline EDSS of ≥ 2.0 . The true proportion could be lower than 45% for ocrelizumab-treated patients who would meet the definition of sub-optimal responders as specified in this protocol. However, the required sample size should be lower than 600 patients to achieve the same precision (i.e., maximum half-width of 95% CI) if the true proportion is actually lower than 45%. This is due to the fact that a lower proportion will have a smaller variance for the estimated proportion than that from 45% and the variance of proportion is maximized when the proportion is 50% (calculation performed using SAS software, Version 9.2). In [Figure 3](#), the sample sizes are displayed from a range of proportions (30% to 50%) with an 80% probability that half-width of 95% CI is at most 4%. For example, if the proportion is 45%, the corresponding sample size is 598.86 (rounded to 600 for recommended number). The ranges of proportion were based on the 2-year proportion of alemtuzumab-treated patients and natalizumab-treated patients who achieved no evidence of disease activity (NEDA) (32% and 55%, respectively). In [Figure 4](#), the sample sizes are displayed similarly to [Figure 3](#), but the

Ocrelizumab—Genentech, Inc.
60/ Protocol MN30035, Version 5

[figure not shown]
half-width of 95% CI is set as 5% for providing additional information concerning the impact of half-width on sample size.

Figure 3 Prob(Half-width of 95% CI \leq 4%) with Sample Size if Expected Proportion=30%–50%

Source: Hartung et al. 2013; Prosperini et al. 2012; Internal OPERA study data.
CI=confidence interval.

Figure 4 Prob(Half-width of 95% CI \leq 5%) with Sample Size if Expected Proportion=30%–50%

Source: Hartung et al. 2013; Prosperini et al. 2012; Internal OPERA study data.
CI=confidence interval.

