6.4 ANALYSIS POPULATIONS

The efficacy analyses will be performed using the intent-to-treat (ITT) population. The per-protocol (PP) population will be used for supportive efficacy analyses (for the primary endpoint and selected secondary endpoints) in order to evaluate the influence of major protocol violators on key efficacy endpoints. The safety population will be used for safety analyses.

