6.7 HANDLING OF MISSING DATA

The following guideline will be used when dealing with missing data related to the protocol-defined event in the primary efficacy endpoint. Patients who complete the treatment period will be considered as having a protocol-defined event if any of the following are reported during the 96-week *study*: at least one protocol-defined relapse, Gd-enhancing T1 lesions, new and/or enlarging T2 lesions, or CDP. Otherwise, the patient will be considered as being protocol-defined event free.

Patients who discontinue treatment early and have at least one event before early discontinuation will be considered as having a protocol-defined event. *Details of missing data handling for patients who discontinue treatment early and do not have any event before early discontinuation* will be specified in Statistical Analysis Plan.

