#### **4.1.2        Modified Intent-to-Treat Population**

The modified ITT (mITT) population is a subset of the ITT population which excludes patients who discontinued ocrelizumab treatment early without any protocol-defined events for reasons other than death and lack of efficacy.

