##### **4.4.1 Primary Efficacy Endpoint**

The proportion of patients who are free from a protocol-defined event during a 96-week period will be calculated and presented along with a two-sided 95% Clopper-Pearson exact confidence interval. Data from unscheduled visits within each respective 24-week interval will be included in the evaluation of the endpoint. Analyses will be performed for the mITT population. Patients are considered to have a protocol-defined event during the 96-week period if they discontinue due to lack of efficacy or death despite without a protocol-defined event as defined below.

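### The Week 96 event-free proportion is estimated in an mITT set whose membership depends on the outcome, and no planned ITT proportion shows how much this matters

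*SAP*

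**What the plan says.** - **Population in the protocol.** Protocol 6.4: "The efficacy analyses will be performed using the intent-to-treat (ITT) population". Section 6.4.1 defines ITT as all dosed patients, including those who withdraw early.
- **Early leavers in the protocol.** Protocol 6.7: "Patients who discontinue treatment early and have at least one event before early discontinuation will be considered as having a protocol-defined event". The next sentence leaves early leavers without an event to the SAP.
- **Population in the SAP.** SAP 4.4.1, on the primary proportion: "Analyses will be performed for the mITT population". SAP 4.1.2 defines mITT as a subset of ITT that "excludes patients who discontinued ocrelizumab treatment early without any protocol-defined events for reasons other than death and lack of efficacy". SAP 4.4.1 scores event-free leavers for death or lack of efficacy as events.
- **Sensitivity analyses.** SAP 4.4.4 repeats the proportion in the per-protocol set. In mITT, it also imputes half of the unconfirmed Week 96 progressions as events. SAP 4.4.2 adds a Kaplan-Meier event-free probability at Week 96. That section puts the time-to-event endpoints on ITT and censors patients without an event at their last MRI or EDSS evaluation.

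**The concern.** Two patients who stop treatment at Week 60 for the same unrelated reason are treated differently. The one with a new lesion at Week 48 stays in the denominator as a failure. The one with clean scans is removed. Early leavers can therefore add failures to the proportion but never successes, which pulls the estimate down even when leaving has nothing to do with the disease.

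The study is single-arm, so this proportion and its 95% interval are the primary result, and no comparator arm carries the same error to offset it. Leavers are not replaced, and Protocol 6.1 states no dropout allowance. The Week 96 proportion is planned only in mITT and in the per-protocol set, so no listed output would show the reader the size of the effect.

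**Working it through.** **1. The plan's own figure.** Protocol 6.1 takes a true proportion of 45%, a half-width of 4 points and 80% assurance, and says "the corresponding sample size is 598.86 (rounded to 600 for recommended number". Solving n·h²/z² = p(1−p) + z₀.₈₀·(1−2p)·√(p(1−p)/n) with p = 0.45, h = 0.04 and z = 1.96 gives 598.3, which agrees. The 4-point half-width is the yardstick below.

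**2. Inputs.**
- True event-free proportion S = 0.45 (Protocol 6.1); 600 treated.
- Share leaving early, d: not given for this study, so assumed 5%, 10% and 20%. The nearest figure in the documents is 3.5% stopping for adverse events on ocrelizumab in the pooled RMS Phase III trials, which is not total dropout.
- Leaving is assumed independent of outcome, equally likely in each 24-week interval, and for reasons other than death or lack of efficacy.
- Cumulative detected events at Weeks 24, 48 and 72: assumed 38%, 45%, 47% (front-loaded) or 20%, 36%, 38% (even).

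**3. Formula.** Let P be the share of leavers with an event detected before leaving. A first-interval leaver has none detected, so:
- front-loaded: P = (0 + 0.38 + 0.45 + 0.47)/4 = 0.325
- even: P = (0 + 0.20 + 0.36 + 0.38)/4 = 0.235

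Expected mITT proportion = S(1−d) / [(1−d) + dP]. Expected mITT size = 600·[(1−d) + dP].

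Worked case, d = 0.10, front-loaded: 0.405/(0.90 + 0.0325) = 0.4343, a bias of −1.57 points, with n = 600 × 0.9325 ≈ 560.

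**4. Results.** Each cell gives front-loaded / even. Coverage is the exact binomial probability that the Clopper-Pearson interval contains 45%.

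| Dropout | mITT estimate | Bias (points) | mITT n | Coverage |
|---|---|---|---|---|
| 5% | 44.2% / 44.5% | −0.76 / −0.55 | 580 / 577 | 94% / 95% |
| 10% | 43.4% / 43.9% | −1.57 / −1.15 | 560 / 554 | 89% / 93% |
| 20% | 41.6% / 42.5% | −3.38 / −2.50 | 519 / 508 | 69% / 80% |

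**5. Cross-check.** With a constant event hazard and leaving times uniform over 96 weeks, P = 0.311 and the bias is −0.7, −1.5 and −3.3 points. In simulation under this model, Kaplan-Meier on all ITT patients, with exact event times and event-free leavers censored, returned 45.0%.

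**6. Direction.** In the same model at 10% leaving, let leavers have k times the hazard of others. The bias is −1.50 points at k = 1, −0.51 at k = 1.5, +0.10 at k = 2 and +0.69 at k = 3. The sign changes near k = 2.

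**7. ITT bounds at 10% dropout.** All event-free leavers scored as events: 0.90 × 0.45 = 40.5%. All scored as event-free: 0.405 + 0.10 × (1−0.325) = 47.3%, or 0.405 + 0.10 × (1−0.235) = 48.2%.

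**8. Kaplan-Meier timing.** MRI is scheduled at Weeks 24, 48 and 96, with visit windows of ±14 days. I simulated 600 patients with the event curves above, zero dropout, a true value of 45% and visit days uniform in the windows. On actual dates the estimate was 48% (front-loaded) to 52% (even) at Day 672, and 48% to 51% at Day 673. By Day 687 it had fallen to 28% and 19%, because late visits leave very small risk sets. On nominal visit days it was 45%.

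**The case against.** **The protocol delegated this.** Protocol 6.7 hands the missing-data rule for exactly these patients to the SAP. A reader might infer that the SAP contradicts a settled protocol rule; the documents do not go that far. What stands is narrower: 6.7 delegated handling and did not alter the population named in 6.4, and deleting the patients does alter it.

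**An ITT analysis is already planned.** A reader might infer that no planned analysis uses the removed patients. That is wrong: the Kaplan-Meier analysis in SAP 4.4.2 does. It is not like-for-like, however. Its event list is relapse, T1 lesion, T2 lesion and confirmed progression, whereas the primary also counts stops for lack of efficacy and death. A gap between the two figures would mix two causes. The per-protocol set is drawn from ITT and Appendix 5 does not list early stopping as a reason for exclusion, so it can contain event-free leavers, but the SAP gives no rule for scoring them.

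**The bias is conservative and may be small.** A reader might infer that the estimate is always too low. That holds only if leaving is unrelated, or moderately related, to disease activity. At 5% dropout the bias is under one point and coverage is close to nominal; the 69% to 80% coverage needs 20% dropout. The analysis is also described as mostly descriptive. All of this stands and limits the severity.

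**Kaplan-Meier should simply become primary.** This is tempting but unsafe on actual visit dates, where step 8 shows a distortion larger than the mITT bias at 10% dropout. The SAP places its visit windows in a separate module, so these documents do not show which times the estimate would use.

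**Conclusion.** The point holds in a limited form. Membership of the primary analysis set depends on the outcome, and neither binary sensitivity analysis measures the consequence. The bias is minor at 5% dropout. At 10% the larger figure is over a third of the planned half-width (1.57/4 = 0.39), and at 20% it is most of it (3.38/4 = 0.85). These sizes rest on assumed dropout, leaving times and event timing, on a true value of 45%, and on leaving being independent of outcome. The low direction is the reasonable expectation, since lack-of-efficacy leavers already count as events, but it is not certain. The change should be made; the trial does not fail without it.

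**What to change.** 1. Beside the mITT result, report the Week 96 proportion on ITT twice: all event-free early leavers scored as events, then all scored as event-free. Leavers for death or lack of efficacy should remain events in both, as in the primary.
2. Tabulate the number removed from mITT by reason for leaving.
3. Align the planned ITT Kaplan-Meier estimate with the primary definition by counting stops for lack of efficacy and deaths as events, and compute it on nominal scheduled-visit times. Do not make Kaplan-Meier on actual dates the primary.
4. State how event-free early leavers in the per-protocol set are scored.

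No new data are needed. The cost is SAP wording and a few table rows, and the reader sees a range beside the single figure.

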#### **4.1.3        Per Protocol Population**

The per-protocol (PP) population will include all patients in the ITT population without key major protocol violations. Key major violations includes key inclusion/exclusion criteria or violations of study conduct that are deemed to potentially affect the efficacy of study treatment. The list of key major protocol violations is finalized prior to final database lock for the study and listed in Appendix 5.

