6.4.2 Per-Protocol Population

The PP population will include all patients in the ITT population who adhere to the protocol. Specific reasons for warranting exclusion will be agreed to by the study team and documented in the SAP.

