## **4.1 ANALYSIS POPULATIONS**

The efficacy analyses will be performed using the intent-to-treat (ITT) or modified ITT (mITT) population. The per-protocol (PP) population will be used for sensitivity efficacy analyses for the primary endpoint only) in order to evaluate the influence of major protocol violators on efficacy of ocrelizumab. The safety analyses will be performed using the safety population.

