#### **4.4.4 Sensitivity Analyses**

The analysis of primary efficacy endpoint described in Section 4.4.1 will be performed for the PP population as a sensitivity analysis. Per study schedule, the last EDSS assessment is at Week 96, such that no subsequent visit with EDSS measurement can be used to confirm an initial disability progression at Week 96. A Sensitivity analysis will be performed for the mITT population to impute 50% of the patients with an initial disability progression at Week 96 as having an event of CDP; the other 50% of these patients as having no event of CDP.

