## **Appendix 5**

### **Reasons for Exclusion from the Per-Protocol Population**

1. Select study inclusion criteria
  - Had more than 3 adequate prior DMTs (IC06)
  - No suboptimal response on the most recent adequately used DMT (IC07)
  - Suboptimal response while on last DMT that is less than 6 months (IC06)
  - Disease duration from first symptom of more than 12 years (Due to previous protocol versions has  $\leq$ 10 years as inclusion criteria, deviation code includes a mixture of deviations of  $>10$  years and  $>12$  years of duration. Thus for this criteria, program on clinical data will be used to identify patients with deviation.)
2. Select study exclusion criteria
  - History of PPMS, PRMS, or SPMS (EC01)
  - Previous treatment with natalizumab within 12 months prior to screening unless failure was due to confirmed, persistent ADAs (EC22)
  - Systemic corticosteroid therapy within 4 weeks prior to screening (EC24)

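### PP is drawn from ITT but the primary analysis uses mITT, so the planned PP comparison mixes a dropout shift with the effect of protocol violators

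*SAP*

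**What the plan says.** SAP 4.4.1 fixes the primary population: "Analyses will be performed for the mITT population". SAP 4.1.2 defines mITT as a subset of ITT that "excludes patients who discontinued ocrelizumab treatment early without any protocol-defined events for reasons other than death and lack of efficacy". Leavers for those two reasons stay in and count as having an event "if they discontinue due to lack of efficacy or death despite without a protocol-defined event" (4.4.1).

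SAP 4.1.3 builds PP from the wider set: "The per-protocol (PP) population will include all patients in the ITT population without key major protocol violations". Protocol 6.4.2 starts from the same place: "The PP population will include all patients in the ITT population who adhere to the protocol". SAP 4.1.3 allows for study-conduct violations as well as eligibility failures and refers to Appendix 5 for the list. That appendix, "Reasons for Exclusion from the Per-Protocol Population", has seven items, four from the inclusion criteria and three from the exclusion criteria. None concerns stopping treatment.

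SAP 4.1 gives the purpose of PP: "in order to evaluate the influence of major protocol violators on efficacy of ocrelizumab". SAP 4.4.4 says how it is used: "The analysis of primary efficacy endpoint described in Section 4.4.1 will be performed for the PP population as a sensitivity analysis".

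On scoring, Protocol 6.7 treats patients who complete treatment without an event as event-free and leaves event-free early leavers to the SAP. For those who leave for reasons other than death or lack of efficacy, the supplied SAP answers only by excluding them from mITT. Its missing-data section (4.8) covers adverse-event attributes and adverse-event and medication dates. The no-event rule in 4.4.1 concerns unconfirmed disability progression. Appendix 3 says that further data-handling rules are in DAP Module 2, which is not among the documents supplied.

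**The concern.** A PP sensitivity analysis is informative when it differs from the primary analysis in one respect, the removal of violators. Protocol 6.4 places the efficacy analyses in ITT, so a PP set within ITT matched them. The SAP moved the primary analysis to mITT and left PP where it was. PP now differs from the primary analysis in two respects: violators are taken out, and the event-free leavers that mITT removed are put back.

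If those leavers count as event-free, PP is pushed upward by an amount unrelated to protocol violations. A PP result above the primary one could be taken to mean that violators had diluted the effect of treatment when it only reflects dropout. A downward violator effect could be masked in the same way.

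**Working it through.** **1. The yardstick.** SAP 2.3 and Protocol 6.1 plan N = 600 for a 95% CI half-width of at most 4 points with 80% probability at an event-free proportion of 45%; the unrounded figure is 598.86. With a Wald interval, the exact binomial probability of meeting the target is 0.741 at n = 597, 0.826 at n = 598 and 0.980 at n = 600, so the plan's figure reproduces to within 2 patients. The Clopper-Pearson interval named in 4.4.1 runs from 40.97% to 49.08% at 270/600, a half-width of about 4.1 points. Four points is therefore a fair scale for what follows.

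**2. Who is where.** For patients with no Appendix 5 violation:

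| Patient | Primary (mITT) | PP |
|---|---|---|
| Has an event | in, event | in, event |
| Completes, no event | in, event-free | in, event-free |
| Stops early, no event, death or lack of efficacy | in, event | in, event |
| Stops early, no event, other reason | out | in, event-free on a literal count |

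Only the last row differs.

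**3. Shift with no violators.** Let N be the ITT size, L the number in the last row and p the mITT event-free proportion.

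- Primary = p
- PP = [p(N − L) + L]/N
- PP − primary = (L/N)(1 − p)

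The documents give no L/N, so the values below are assumptions. At p = 0.45:

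- L/N = 3%: 0.03 × 0.55 = +1.65 points
- L/N = 5%: 0.05 × 0.55 = +2.75 points
- L/N = 10%: 0.10 × 0.55 = +5.5 points

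In whole patients with N = 600: L = 30 gives 256/570 = 44.9% in mITT and 286/600 = 47.7% in PP; L = 60 gives 243/540 = 45.0% and 303/600 = 50.5%.

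**4. Range of p.** Protocol 6.1 cites 32% and 55% for two other treatments. At L/N = 5% the shift is 0.05 × 0.68 = +3.4 points or 0.05 × 0.45 = +2.25 points.

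**5. When it reaches the planned half-width.** 0.04/0.55 = 7.3% of ITT, or 44 of 600 patients.

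**6. With a violator effect present.** Assume 5% violators, spread evenly over leavers and others, with an event-free rate 20 points below non-violators. Non-violators in mITT then have 0.45 + 0.05 × 0.20 = 0.46, so the violator effect is +1.0 point. At L/N = 5%, PP = 0.46 × 0.95 + 0.05 = 48.7%, and PP − primary = +3.7 points. Most of that is dropout. A PP set drawn from mITT would give 46.0%, which is +1.0 point.

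**7. Can it be undone?** By the definition in 4.1.2, everyone in ITT but outside mITT is event-free at discontinuation. SAP 4.2 reports the population sizes and 4.4.1 gives the mITT count x. With leavers scored event-free, the ITT proportion is (x + N_ITT − n_mITT)/N_ITT; for L = 30 this is (256 + 30)/600 = 47.7%. In the example of step 6, ITT = 0.45 × 0.95 + 0.05 = 47.75%, and PP − ITT = 48.7 − 47.75 = +0.95 point. That is the violator effect with the leavers included (0.95 × 1.0).

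**The case against.** The strongest reply is step 7: planned outputs allow a matching ITT proportion to be rebuilt, so the violator effect is not lost. This stands. A reader might infer that PP can never isolate violators, and that would go too far. The reconstruction does need the scoring used in PP, and the plan does not present this comparison.

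A second reply is that the scoring is settled, because 4.4.1 turns only lack-of-efficacy and death withdrawals into events and 4.4.4 reruns that analysis. As a literal reading this also stands. A reader might infer that the direction of the shift is open, since scoring leavers as events would give −(L/N)p, or −2.25 points at 5%. No passage scores them as events, so the text supports only the upward shift. The literal count is still a default and not a written rule. ITT keeps patients with no assessments at all (4.1.1), and such a patient would be counted in PP as event-free for 96 weeks.

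Third, the rule may be in DAP Module 2. It may, so the most that can be said is that the supplied SAP text does not state it.

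Fourth, 4.1.3 mentions conduct violations, which could in principle cover early stopping. Appendix 5 as supplied lists none. Similarly, 4.4.4 could be read as carrying the mITT restriction into PP, but neither it nor 4.1.3 says so, and 4.1.3 names ITT.

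Finally, the study is single-arm and mostly descriptive, and no decision rule uses PP. That limits the consequence but leaves the comparison mismatched. The Kaplan-Meier analysis censors event-free leavers, but it is a separate analysis and does not correct PP.

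**Conclusion.** The point holds as a misleading planned comparison. As written, PP minus primary contains an upward dropout shift of about (L/N)(1 − p) in addition to the violator effect that PP is meant to show. At p = 45% this is +2.75 points for 5% event-free leavers and +5.5 points for 10%, against a planned half-width of 4 points. These sizes rest on the literal 4.4.1 count and on an assumed leaver share. The 3.5% discontinuation rate for adverse events in the pooled RMS trials (Protocol 1.2.1.2) is not all-cause and does not bound that share. The violator rate and effect in the worked example are also assumed.

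A reader might infer that the primary result is biased by this mismatch. It is not: the primary estimate does not use PP. The harm is confined to how PP is read, and it is worth correcting because the edit is small.

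**What to change.** Before database lock, do one of the following.

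- **PP within mITT.** In SAP 4.1.3, define PP as mITT patients without key major protocol violations, and record the departure from Protocol 6.4.2. Only violators then differ between the two analyses. Cost: a short SAP edit and minor programming on data already collected, and a somewhat smaller PP set. The drawback is that PP inherits mITT's outcome-dependent exclusion, in which leavers without an event go and leavers with one stay.
- **PP within ITT, with a matched comparator.** Keep the protocol definition, state in 4.1.3 or 4.4.4 how event-free early leavers are scored, and compare PP with the primary-endpoint proportion in ITT under the same rule. Cost: one sentence and one extra tabulation.

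If DAP Module 2 already holds a scoring rule, bringing it into the SAP supplies the sentence for the second option, but the ITT comparator is still needed.
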